Parts a and b of the SIT approach require SHCP to complete a MEAH questionnaire and state the most significant difficulty they are experiencing at that point in time (past research identified that this would focus on the COVID-19 impact on the ability to work, relationships or include the combination of difficulties from COVID-19 alongside additional stressors such as family bereavement). The MEAH questionnaire will be email to [name] before a single e-based (e.g., Skype or Zoom) or telephone call. The single 20-minute conversation will include questions taken from our successful pilot research. Following this, part c will commence using an e-learning intervention based on past pilot research. We have developed a presentation to train SHCP to use a story-telling approach to for patient's management; this will additionally include the rationale for the use of MEAH including the science and theory. Finally, SHCP will be provided with a e-learning presentation that summarises coping strategies identified from the interview in part a. The unpinning rationale for SIT approach is that we support the mental health of SHCP and also and train them to apply the approach in clinical practice to improve patient outcomes.

Our primary aim is to assess the effectiveness of the intervention on levels of depression and anxiety in SHCP. Other outcomes of interest relate to confidence of SHCP achieving quality indicators of SHCP-patient communication, SHCP attitudes, empathy, hope, NHS related cost-savings utilisation, work outcomes and quality of life.

The planned study requires SHCP to be allocated to either a control group or the intervention group (with MEAH training). SHCP assessment will take place before and after the intervention and again at 12-weeks. The waiting list control group will receive the MEAH training at 12-weeks. Follow up assessment for both groups will be at 3 months. The main purpose of this study is to investigate the content of the SIT e-learning training on SHCP and gain an insight into the effect of this inexpensive and accessible, evidence-based training on patient outcomes. The most direct benefits include; (a) improved mental health for SHCP and patients. (b) empowerment of patients to seek positive coping behaviours, reducing the need for additional costly healthcare services for SHCPs and potentially patients. (c) increase resilience of SHCP and reduced burn out (d) improve patient satisfaction and (e) reduced need for pharmacological approaches to treat mental illness SHCP (f) reduced work absence and improved productivity of SHCP .

Introduction

Understanding and supporting the mental health of frontline workers during the COVID-19 is fundamental to the health of staff and patients. Within the hospital setting SHCP face

environments of extreme stress caused by COVID-19, this includes access to appropriate personal protective equipment, being deployed to new and unknown practice environments, a lack of updated information, being exposed to the virus and then concerns about perhaps unknowingly transmitting to a family member, peers or others (Shanafelt et al., 2020). Outside the work setting opportunities to support others within their family circle are impacted by government legislation of lockdown and social distancing. As a result, SHCP are experiencing profound psychological problems, including anxiety, depression and distress; a direct result of caring for patients who have COVID-19 (Pfefferbaum and North, 2020; Lui et al., 2020).

Research is therefore urgently needed to investigate the mental health of frontline staff (Holmes et al., 2020), including both training to help SHCP cope with patients' emotional concerns, anxiety and panic (Chen et al., 2020), and mental health screening for all SHCP (Pfefferbaum and North, 2020), including support mechanisms to help SHCP manage the extreme and unforeseen challenges of a pandemic (Shanafelt et al., 2020). Benefits would see improved work-related outcomes of SHCP, improved quality of care and as a result cost effective treatment for patients. Flexible, cost-effective and widely accessible approaches are urgently needed, with e-learning being an obvious choice during the COVID era. Evidence supports this with e-learning associated with improved standardisation of instruction and enhanced cost-effectiveness compared to face-to-face instruction (Cendan and Locke, 2012). Moreover, e-learning methods provide SHCP an opportunity and means to reflect and self-correct their actions and behaviours (McDonald et al., 2018). The benefits of this include enhanced resilience and experience of interactions resulting in reduced stress. E-learning interventions offer an alternative solution to screen and support the mental health of SHCP, bypassing the need for direct contact with trainers (Pfefferbaum and North, 2020). Thus, this e-learning offers considerable potential to both support the mental health of SHCP and train them to manage stress during challenging interactions within their clinical environment. Our e-learning training approach, the Screen, Intervene, and Train (SIT) approach to care could easily be scaled up and implemented effectively on a national level (Duan et al., 2020). Our pilot research into the SIT approach has contributed to the creation of an evidence based and short e-learning training which could achieve the needs identified at a population level.

The SIT approach was developed from the model of emotions, adaptation and hope (MEAH). The MEAH was the final development of a set of 12 reviews that focused on the (re)conceptualisation hope and psychological adaptation. This work was conducted across various chronic conditions (e.g., Parkinson's, Multiple Sclerosis, Stroke, Spinal Cord Injury) and palliative conditions (e.g., Motor Neurone Disease and Cancer) and subsequently supported by empirical research on chronic and palliative conditions led by [name]. The MEAH reconceptualises psychological adaptation and represents the key psychological features of common story plots identified from illness stories across various illness experiences (Soundy, 2018). The MEAH screening tool was developed to capture psychological responses to a personally named difficulty faced within a short period of time (30 seconds). Pilot research has identified these difficulties as the experience of suffering or loss, the impact of change and an uncertain future and changes in meaningful social identities, activities or relationships. This is constant with the structure and framework for hope (Soundy et al., 2014). The benefit of this was that SHCP can use the difficulty to support a brief personalised intervention with as little as one question if needed, meaning enhanced and immediate therapeutic interaction. By analysing data gathered from pilot studies, patients and participants used an iterative process to develop a screening tool (MEAH Scale). The three critical applications of the MEAH together are referred

to Screen, Intervene and Train “SIT” approach to care:

- a) Screen and Intervene: The MEAH can be used as a unique screening tool for SHCP as part of training (or subsequently in routine clinical practice by SHCP). The MEAH screening tool focuses on a self-selected difficulty and allows the SHCP a chance to understand the MEAH model through direct and personal experiences that can be shared. Being able to talk about this difficulty using specific questions was associated with increased hope, enhanced acceptance as well as positive changes in emotions. The questions of the tool are derived from two validated scales (Soundy et al., 2016; Russell, 1980) that provide the central psychological constructs associated hope, adaptation and emotions. The screening and intervening aspects of the training uses a form of pedagogy known as ‘real play’ (Norris et al., 2019). Our pilot research¹ in May 2020 involved screening and supporting the psychological adaptation and hope of student physiotherapists (n=19) when the COVID-19 crisis resulted in significant changes in their professional education. The research included a mixed methods study and identified the impact of a student talking and responding to questions related to the MEAH. The study demonstrated significant and positive changes in hope, adaptation or emotions across student participants. This demonstrates the importance of being able to share personalised experiences using the MEAH scale as a way of supporting the mental health of SHCP. This provides evidence to support the use of MEAH as a brief screening and intervening tool to initially support SHCP with a single Skype/Zoom or phone call at the start of the training.
- b) Train: The MEAH offers the science as to why narrative-based interventions have been associated with improvement in patient mental well-being outcomes. Our recent research² to assess the training of SHCP has included a sequential 2-phase mixed methods study involving student physiotherapists. The e-learning included a 1-hour training session, providing proof of concept and piloted since the outbreak of COVID-19. Findings suggest that SHCP who use a narrative-based intervention experienced perceived improvements in recognised communication skills that enhance therapeutic conversations. Notably a consistent reduction in personal distress from pre-post and from pre-6-week follow up in relation to challenging interactions was found. Physiotherapist participants had applied the training and were more confident in difficult interactions.

Together these two applications (screen, intervene and train) of the MEAH model have been combined into a single e-learning approach to support the mental health of SHCP and to train SHCP to manage patients in very short time period (under 2 hours). Having completed the SIT approaches we would be able to consider effectiveness of the training during SHCP-patient interactions by focusing further on emotions, adaptation and hope.

It is important to note that all stages of the SIT approach have been developed using electronic resources, and as such the planned study methods are compliant with current legislation on social distancing, whilst being scalable to achieve a wider reach of SHCP across the NHS and other practice settings in the post COVID era across the UK. The additional benefit of this work

¹ Ethical approval was gained from University of Birmingham ethics committee reference: ERN_20-0565.

² Ethical approval was gained from University of Birmingham ethics committee reference: ERN_18-1970B and ERN_18-1970C. Online protocol number: ISRCTN 13368968

is that once trained, SHCP can apply the training at a patient level, or as part of personalised medicine and we would be able to pilot the effectiveness of the training on patients using a multi-centre quasi-experimental design.

Our research to date underpins our rigorously developed e-learning training which has been tested as a proof of concept in a single application and has the potential, following further research to be applied to the NHS and then more globally. The proposed research seeks to combine the above two applications for a novel study that can be offered across all frontline SHCP.

Aims and Objectives

The aim of this study is to investigate the impact of a 2-hour MEAH e-learning training session on depression and anxiety of SHCPs.

Objectives

1. To explore changes in depression and anxiety as a primary outcome measure across three time points (pre-intervention, post intervention, at 12-weeks) for all front-line SHCP during the screening and intervening phase. To compare the intervention and control at the pre-, post- and follow up time points
 2. To identify longer term outcomes for the SHCP intervention group at 6 months
 3. To examine changes in secondary outcome measures on SHCP including quality of life, stigma, communication, hope, and empathy.
 4. To identify any differences between SHCP cohorts (e.g. doctors, speech and language therapist, nurses, occupational therapists and physiotherapists)
- To illuminate the benefits of our e-learning approach on the SHCP mental health.

Main Study

We report this according to the SPIRIT guidelines (Chan et al., 2013).

Design: A multi methods study involving a randomised trial with a waiting list inactive and active control group. Following the CONSORT recommendations and flow diagram (Schulz et al., 2010). See Figure 1 for trial design and Table 1 for Gantt Chart. Qualitative data will be generated through the training which will further help understanding experiences of COVID-19 and a qualitative study involving semi-structured interviews to consider the benefit of the study will be undertaken from week 12. PPI involvement has contributed to this across different stages see below.

Study setting: The trial will be run from the following Universities: University of Birmingham, Birmingham City University, Coventry University, Brighton University, Southampton University and Oxford Brookes University.

Contacts at the following Universities have been made to agree access:

University of Birmingham

Existing contacts: [name], [name], [name] – Physiotherapy here at Birmingham

New requests: Nursing – [name], Medicine – [name].

Brighton University – [name] Physiotherapy Program

Southampton University - [name] lecturer in health sciences here and PT, and [name]

Birmingham City University - [name] Speech and Language therapy course lecturer.

Oxford Brookes University. - [name] (programme Lead) and [name] (Subject coordinator) for the physio programmes at Brookes.

Coventry University for Occupational Therapy Program – [name] [name]

Nottingham University – Occupational Therapy [name].

Eligibility; Any SHCP currently **studying at on a course from the above Universities.**

Approach and Recruitment; An initial email contact (Appendix A) will be sent to all SHCP with an information sheet via email (See Appendix B). After 48 hours individuals will be recruited.

Sampling and sample size; Any SHCP currently studying and working in COVID-19 units. Pilot research identified significant impact on student communication and a medium effect size is expected. Using Cohen's (1988) tables with an alpha of 0.01, $d = 0.5$ (a medium effect) and beta of 0.9 we will recruit 94 SHCP per group to take part in this research. This will give a total of 120 SHCP and we will add in a 10% margin ($n=20$) for dropout or incomplete data. This gives a total of 140 SHCP to be randomised per arm or 280 in total. We will try and ensure a mixed sample with SHCP from different allied health professional groups using purposive sampling.

Sequence generation; Random number calculator with randomly selected block sizes (Efird, 2011).

Allocation concealment; undertaken by e-links not known to the researcher

Sequence generation; We will replicate the pilot research and include a random number calculator with randomly selected block sizes (Efird, 2011). Randomisation undertaken by a member of the research team separate from the study will allocate SHCP to an intervention control group using a random number generator.

Blinded assessor; Only blinded assessment will take place. Before randomisation a blinded assessor (lecturer in physiotherapy or research student) will distribute questionnaires. The pre-recorded e-learning programme has been prepared by [name] who developed and prepared all pilot studies. Following the completion of the training an assessor who is blinded to treatment arm will organise and collect follow-up assessments.

Data collection methods: Before data collection starts SHCP will be shown the information sheet via email and asked to consent (Appendix B). A baseline measurement will take place (Appendix C). The baseline measurement will take place over a secure electronic data capture system called Research Electronic Data Capture (REDCap). Following this, students in each group will receive the training. Once the training is complete students will again fill in the measurement tools using REDCap. The research associate will send out two email reminders to any participant who doesn't fill in the forms.

Intervention: The SIT intervention will include a single screening interview taking 20 minutes with [name]. Following this the participant will be sent a pre-recorded e-based training session. The lecture takes 45 minutes. The indicative content considers examples of interactions, the science behind the MEAH, the use of screening and how to engage in a brief narrative-based intervention within practice. It has the same components as the pilot studies, although adapted into one training session. The final part of the training for SHCP will include an e-learning presentation. The presentation will provide an analysis of the screening calls. This will reveal the most common difficulties and stories expressed within screening and will

summarise the difficulties that were challenging to adapt to, illustration of how the MEAH is important for this understanding and the most common coping strategies identified (this was undertaken and achieved as part of the pilot research to consolidate learning). The principles are that sharing this information will provide direct access to others experiences which has been associated with enhanced mental health outcomes (Ooms et al., 2016; Soundy et al., 2019). The benefit of this is SHCP can access effective coping strategies that promote mental health and psychological well-being outcomes. This entire process will take a maximum of two hours to complete at a pace and time that is convenient to the participant.

Inactive control group 1: an inactive waiting list control group will be used. Individuals in this group will receive or be offered the SIT intervention at week 12.

Active control group 2: an alternative e-intervention will be used which includes a 45 minutes pre recorded lecture. Individuals in this group will receive or be offered the SIT intervention at week 12.

Outcome measures for SHCP;

See Appendix C for all outcome measures

Demographics; Age, gender, professional group, type of course, year of course. Time experience of working in a COVID-19 setting in months.

Primary outcome measure for SHCP:

The Hospital Anxiety and Depression Scale (HADS: Zigmond and Snaith, 1983). A 14-Item questionnaire that assesses depression and anxiety.

Secondary outcomes measures for SHCP;

(a) The SF-12 Quality of life questionnaire (Ware et al., 1995). A 12-item questionnaire that assesses quality of life.

(b) The 15-item open minds scale for health care providers (Kassam et al., 2012; Modgill et al., 2014). This score uses a five-point Likert scale and a total score is calculated which exists between 15-75. Five items are reversed coded. Higher scores signify more stigmatising attitudes and intentions of behaviour.

(c) Froehlich Communication Survey (Froehlich et al., 2016). A 25-item scale that assesses communication. The pilot research identified a significant change across time from this outcome.

(d) The interpersonal reactivity index (Davis, 1983). A 28-item scale that uses a 5-point Likert scale that measures empathy. Pilot research showed a reduction in personal distress for challenging interactions.

(e) The Adult Hope Scale (Synder 1991). A 12-item measure of respondents hope.

(f) The MEAH version 3.3 which is made up of the hope and adaptation scale (Soundy et al., 2016) and the circumplex model of affect (Russell, 1980).

The total time to complete the primary and secondary outcome measure is about 10 minutes. After this there will be a 12 week, 6-month follow up for primary and secondary outcome measures.

Other qualitative data generated:

The screening at the beginning of the intervention will be recorded across a 20-minute

Skype/Zoom interview (see Appendix D) to reflect on the difficulty identified within the MEAH screening tool version 3.3. This replicates the pilot screening work which produced significant improvements in psychological well-being. The summarised data will be presented to SHCP following the intervention and can be used for a qualitative peer reviewed publication.

Finally, a single semi-structured interview at week 12 will be undertaken to detail SHCP perception of the processes. See Appendix E for the interview schedule

Participant timeline:

The participant timeline is based on evidence from the pilot studies showing an efficient timeline. This included ethical approval given in April 2020 and submission of one study by late May 2020 and the second is on course for late June 2020. Given this the following has been planned, **maximum** time periods are as follows:

Ethical approval submitted: September 2020

Trials registration submitted and completed: October 2020

Advertisement of study: October 2020

Enrolment and randomisation: October 2020-November 2020

Post assessment completed by: December 2020

12-week follow up completed by: February 2021

Main Publication submitted for publication: March 2021

24-week intervention group follow up completed by: May 2021 (analysis completed by trials unit other staff costs covered by University)

Follow up publication: June 2021

Other publications: September 2021.

Data management: The research associated will use the University REDCap system to access the data and only work on a University password protected computer.

Statistical methods; For the main study and sub-study descriptive statistics will be used. Confidence intervals will be used to consider change. A factorial ANOVA (a parametric statistical technique which can assess change in one test rather than needing to perform many) will be used to test group differences across outcome measures. An ANOVA will consider the change in scores across time for the intervention group. All qualitative data will be analysed using a thematic analysis (Braun and Clarke, 2006).

Data monitoring: [name] will report any adverse events to University program leader for consideration. Any program leader will be able to stop the study if required. No adverse events were reported across all pilot research. All adverse events will be reported to the steering group committee.

Ethics: We will adhere to the; Research Governance Framework (Department of Health 2005), Declaration of Helsinki (World Health Association, 2013) and University of Birmingham Code of Practice for research (University of Birmingham 2018) and General Data Protection Regulation (2018).

Protocol amendments: [name] will report any protocol amendments.

Consent: the research associate will ensure consent is obtained from participants.

Confidentiality: All data will be stored anonymously on the University of Birmingham computer. Declaration of interest: None are declared.

Access to data: only the research team will have access to the full data.

Ancillary and post-trial care: This will be reported by [name] to program leads if required.

Deliverables

Benefits within the Hospital setting

- Reduced depression and anxiety across SHCP
- Positive changes in hope, psychological adaptation and emotions in relation to a specified difficulty
- Increased resilience and decreased burn out in staff
- Enhanced interactions that are supportive and able to empower patients to be more autonomous
- Increased patient satisfaction
- Potential to decrease reliance on pharmacological approaches
- Reduced work absence and improved work productivity
- Identification of basic NHS-related cost savings

[figure not shown]
Multiple Publications

- A main publication on the trial results and qualitative publication using follow up interviews; Submitted to a journal like British Journal of Psychiatry impact factor: 7.33.
- A qualitative publication around the narratives used within a discussion board set up as part of the training. Submitted to a well-established SHCP related journal like Physiotherapy: impact factor 3.
- A secondary publication around the application of the training for patients across a single session. This will act as pilot research for development of the tool. Submitted to a well-established SHCP related journal like Physiotherapy: impact factor 3.

Training in other settings

- Offer the training to any UK hospital if successful and pilot results are repeated
- Be able to offer the training to alternative settings as required
- Be able to identify a training guide for teaching the intervening stage to professionals who want to use the MEAH screening

Figure 1.0 CONSORT 2010 Flow Diagram

References

- Australian Physiotherapy Association 2016 Position Statement: Scope of Practice. https://australian.physio/APAWCM/Advocacy/Position_Statements.aspx.
- Chan A-W, Tetzlaff JM, Altman DG, Laupacis A, Gøtzsche PC, Krleža-Jerić K, Hróbjartsson A, Mann H, Dickersin K, Berlin J, Doré C, Parulekar W, Summerskill W, Groves T, Schulz K, Sox H, Rockhold FW, Rennie D, Moher D. SPIRIT 2013 Statement: Defining standard protocol items for clinical trials. *Ann Intern Med* 2013;158:200-207.

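### The protocol names no single primary HADS score, time point or comparator, so the 0.01 error rate used for sizing is not tied to any one test

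*Protocol*

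**What the plan says.** Objective 1 (Aims and Objectives) reads "To explore changes in depression and anxiety as a primary outcome measure across three time points": before the intervention, after it, and at 12 weeks. It continues: "To compare the intervention and control at the pre-, post- and follow up time points". The word control is singular there.

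The Design paragraph and the control-group paragraphs describe two controls, an inactive waiting list and a second one: "Active control group 2: an alternative e-intervention will be used". The primary outcome paragraph names the HADS and says that it covers depression and anxiety. It does not say whether the total score or the two subscales will be analysed.

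Sampling and sample size assumes "alpha of 0.01, $d = 0.5$ (a medium effect) and beta of 0.9", which describes one standardised difference between two groups.

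Statistical methods plans a factorial ANOVA for group differences and describes it as a technique "which can assess change in one test rather than needing to perform many". It adds a separate ANOVA over time within the intervention group. It gives no significance level and does not say which effect is the primary one.

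**The concern.** A sample size calculated for one test at 0.01 describes the trial's error rate only if one test decides the primary question. Here the primary objective covers two constructs and two post-baseline times, and the design has two controls. A report could therefore claim primary success on anxiety or depression, early or at 12 weeks, against a waiting list or an active lecture. These are different claims. Beating a waiting list is not evidence of beating another e-learning session.

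The reason given for the ANOVA suggests that multiplicity has been dealt with, and it has not. Choosing the primary score, time and comparator defines the objective itself. It is not an analysis detail that would ordinarily be left to the statistical analysis plan.

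**Working it through.** **Inputs.** From Sampling and sample size: alpha 0.01, d = 0.5, and "beta of 0.9 we will recruit 94 SHCP per group". The 0.9 is read as power. Sidedness is not stated; two-sided is assumed because it reproduces the protocol's figures.

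**Step 1: what the sizing covers.** n per group = 2(z₁₋α/₂ + z_power)² / d².
- 90% power: 2(2.576 + 1.282)² / 0.25 ≈ 119.0, so 120 per group.
- 80% power: 2(2.576 + 0.842)² / 0.25 ≈ 93.4, so 94 per group.

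The printed 94 therefore matches 80% power. The 120 that appears next, called a total, is the 90% figure per group. That inconsistency is a separate matter. Either way, the calculation is for one two-group test at 0.01.

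**Step 2: how many primary comparisons.** Scores × post-baseline times × comparators:

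| Reading | Count |
|---|---|
| HADS total, one control comparison | 1 × 2 × 1 = 2 |
| HADS total, two controls | 1 × 2 × 2 = 4 |
| Two subscales, one control comparison | 2 × 2 × 1 = 4 |
| Two subscales, two controls | 2 × 2 × 2 = 8 |

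**Step 3: chance of at least one false positive at 0.01 per test.** Under independence this is 1 − 0.99^k. Positive correlation lowers it.
- k = 2: 1.99%.
- k = 4: 3.94%.
- k = 8: 7.73%. Independence cannot hold here, because contrasts against the two controls share the SIT arm.

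For k = 8, one million simulated sets of two-sided z statistics were drawn. The correlation between the two contrasts was 0.5 (shared arm), and a common value was assumed for the subscale and time correlations:

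| Assumed subscale and time correlation | Family-wise error |
|---|---|
| 0.3 | 7.1% |
| 0.5 | 6.7% |
| 0.7 | 5.8% |
| 0.8 | 5.1% |

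**Step 4: does the ANOVA reduce this to one test?** A group-by-time ANOVA gives at least a group F test and an interaction F test for each outcome. Treating these as independent tests at 0.01 gives about 2% for one outcome (k = 2) and 3.9% for two (k = 4). Neither F test says which control SIT differs from, so contrasts are still needed.

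**Step 5: what the remedies cost.**
- One named contrast at 0.01: 120 evaluable per arm for 90% power, unchanged.
- Two co-primary subscales: the first Holm step uses 0.01/2 = 0.005, so z = 2.807. With 120 per arm the expected z is 0.5 × √60 = 3.873, and power is Φ(3.873 − 2.807) ≈ 86%, against Φ(3.873 − 2.576) ≈ 90%. Restoring 90% at that threshold takes 134 per arm.

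**The case against.** The best defence is that the protocol never sets out a family of eight tests. It speaks of one outcome measure and one instrument. Objective 1, Appendix A and the total of 280 (two arms of 140) all read as one control group. With the HADS total and one control comparison, only two post-baseline comparisons remain. If contrasts followed a significant omnibus F test among exactly three groups, that gate would itself control error across the pairwise contrasts. No passage says that one positive result is enough, and requiring all to be positive would not inflate the error. Because 0.01 is strict, even the largest correlated figure is close to a conventional 5%. A multiplicity procedure may also stand in a statistical analysis plan that is not shown.

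Much of this stands, and it limits the size of the point. It does not remove it. The protocol states neither a gate nor an all-must-win rule, and a gate across groups would not cover scores or times. It does not present 0.01 as an allowance for multiplicity. The verb explore in Objective 1 does not make the objective exploratory either, since the protocol's opening summary states a primary aim of assessing effectiveness.

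A reader might infer three stronger claims that the documents do not support:
- **Exactly eight primary tests with 7.7% error.** Eight is only the largest reading, and 7.7% needs an independence that the shared arm rules out.
- **An error rate of 21% to 34%.** This comes from testing each of the eight at 0.05, a level that the protocol nowhere states.
- **A planned significance test at baseline.** The mention of the pre time point fits equally well as one level of the time factor in the ANOVA.

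**Conclusion.** The point holds in a limited form. The primary objective leaves the HADS score, the time point and the comparator open, while the sizing assumes one two-group test at 0.01. The implied false positive rate is about 2% (two tests), at most 3.9% (four) or about 5% to 7% (eight).

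These figures assume two-sided tests at 0.01 each and success on any one positive result. The range for eight also rests on assumed subscale and time correlations of 0.3 to 0.8, and 0.5 for the shared arm. The inflation is modest in absolute terms. The larger weakness is that the trial's primary claim is not fixed, and the stated reason for thinking that one test suffices is incorrect.

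**What to change.** In Objective 1 and the primary outcome paragraph, name one primary HADS score, one time point and one primary contrast. An example is the HADS total at 12 weeks, SIT versus waiting list at 0.01, followed by SIT versus active control at 0.01 only if the first is significant. The sponsor should choose which score, time and order. Make the other scores and times secondary. Delete the one-test rationale from Statistical methods. State that the comparison at the pre time point is descriptive, or that the baseline score enters as a covariate, and that it is not a significance test.

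The cost is that some comparisons lose primary status, and the second contrast becomes conditional on the first. No sample size increase for multiplicity is needed: 120 evaluable per arm still gives about 90% power for each contrast taken singly. Testing both controls does require that number in each of three arms, 3 × 120 = 360 evaluable, whereas the stated 280 covers two arms. That inconsistency has to be resolved in any case.

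If the sponsor prefers to keep both subscales primary, Holm across the two is workable. The protocol should then state that power at the first step falls from about 90% to 86% with 120 evaluable per arm.
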